1. INTRODUCTION

The purpose of this Statistical Analysis Plan (SAP) is to provide comprehensive and detailed descriptions of the methods and presentation of data analyses proposed for Arcturus Therapeutics, Inc. Protocol ARCT-165-01 (A Phase 1/2 Randomized, Observer-Blind Study of the Safety, Reactogenicity, and Immunogenicity of 3 SARS-CoV-2 RNA Vaccine Candidates in Adults Previously Vaccinated and Not Previously Vaccinated Against SARS-CoV-2). Descriptions of planned analyses are provided in advance of breaking the study blind in order to reduce the risk of bias. The endpoints and statistical methods applied in the design and planned analyses of this study are consistent with the International Council for Harmonisation (ICH) guidelines *Statistical Principles for Clinical Trials (E9)* (1998) and *Statistical Principles for Clinical Trials: Addendum: Estimands and Sensitivity Analysis in Clinical Trials (E9[RI])* (2017), as well as the US Food and Drug Administration (FDA) guideline *Development and Licensure of Vaccines to Prevent COVID-19* (2020).

Cohorts A and B will be analyzed independently for the final analysis. The SAP will be finalized prior to data analysis and before treatment unblinding and database freeze for Cohort B. The SAP may be amended to further describe planned analyses for Cohort A prior to database lock (DBL). This SAP will provide comprehensive details of the tables, figures, and listings to be presented in the Clinical Study Report (CSR). Any changes between the statistical methods provided in the clinical study protocol and this SAP will be explained herein; any changes or deviations from this SAP relative to the final analysis will be fully documented in the CSR. Minor changes or deviations from the templates for tables, figures, and listings need not be documented in the CSR.

2. STUDY OBJECTIVES

2.1 Primary Study Objectives

The primary objectives of this study are to describe:

- The safety and reactogenicity of three investigational severe acute respiratory syndrome-coronavirus-2 (SARS-CoV-2) self-amplifying ribonucleic acid (RNA) vaccines; and
- The immunogenicity (antibody responses) of three investigational SARS-CoV-2 self-amplifying RNA vaccines.

2.2 Exploratory Study Objectives

The exploratory objectives of this study are to:

- Describe and compare the cell-mediated immune response to different variants of SARS-CoV-2 viruses following vaccination with three investigational SARS-CoV-2 self-amplifying RNA vaccines;
- Summarize the incidence of coronavirus disease 2019 (COVID-19) cases in enrolled study participants; and

- Provide sera for use for exploratory passive transfer studies in animals.

3. INVESTIGATIONAL PLAN

3.1 Overall Study Design

This is a randomized, observer-blind, two-cohort study evaluating the safety, reactogenicity, and immunogenicity of three investigational SARS-CoV-2 self-amplifying RNA vaccines. This study is intended for execution in one or more clinical study sites in one or more of the following countries – Singapore, South Africa and the United States (US).

The study will initially enroll approximately 72 adult participants divided into two cohorts of 36 adult participants based on previous vaccination status against SARS-CoV-2.

Cohort A will include a total of 36 adult participants ≥ 21 to ≤ 65 years of age who have not been previously vaccinated (vaccine-naïve) with a SARS-CoV-2 vaccine. Cohort A is further subdivided into two vaccine-naïve sub-cohorts. Participants in Sub-cohort A1 (n=12 participants, seronegative) will be randomly assigned (1:1:1) to receive two 5- μ g doses of ARCT-165, ARCT-154, or ARCT-021. Participants in Sub-cohort A2 (n=24 participants, seropositive) will be randomly assigned (3:1) to receive two 5- μ g doses of ARCT-154 or ARCT-021 respectively. Participants in both sub-cohorts will receive the first dose on Day 1 and the second dose on Day 29.

Cohort B will include a total of 36 adult participants ≥ 21 to ≤ 65 years of age who have been previously vaccinated (5 months or longer prior to study enrollment) with the BNT162b2 (Comirnaty) SARS-CoV-2 vaccine. Participants will be randomly assigned (1:1:1) to receive one 5- μ g dose of ARCT-165, ARCT-154, or ARCT-021. Study vaccine will be given as a single dose on Day 1.

The first 3 participants (sentinel participants) enrolled in Sub-cohort A1 and Cohort B will be randomly assigned (1:1:1) to one of three study vaccines (ARCT-021, ARCT-154, and ARCT-165) administered in a blinded, parallel dosing fashion. For Sub-cohort A2, the first 4 participants (sentinel participants) enrolled will be randomly assigned (3:1) to ARCT-154 or ARCT-021 administered in a blinded, parallel dosing fashion. Safety in each of these initial cohort participants (3 participants in Sub-cohort A1, 4 participants in Sub-cohort A2, and 3 participants in Cohort B) will be evaluated for three days after vaccination. The safety data will also be reviewed by a blinded Safety Review Committee (SRC) prior to the start of dosing of remaining participants in these cohorts. The study will also include the use of pausing and stopping rules that may pause or stop dosing of study vaccination based on any unexpected safety concerns. Further details of the pausing rules are provided in Section 4.2.4 of the clinical study protocol.

Throughout the study, and up until 12 months after last dose of study vaccine, participants will be regularly assessed for safety using solicited and unsolicited adverse event (AE) collection, concomitant medication collection, physical examinations, vital signs, and safety laboratory assessments as specified in the schedule of assessments in Appendices 1 and 2 of the clinical study protocol.

[figure not shown]
Participants will also undergo blood sampling for antibody and cell-mediated immunity (CMI) responses to SARS-CoV-2 vaccines as well as for collection of sera for possible use in non-clinical passive transfer studies. Participants who develop symptoms of COVID-19 or who are exposed to someone who has been diagnosed with COVID-19 or SARS-CoV-2 infection will undergo testing to determine if the participant has SARS-CoV-2 infection.

Safety, immunogenicity, and COVID-19 assessments will be performed through the duration of study participation as specified in the schedule of assessments in Appendices 1 and 2 of the clinical study protocol.

The end of study (EOS) is defined as the date on which the last participant completes the last study visit (including the EOS visit and any additional long-term follow-up). Any additional long-term follow-up that is required for monitoring of the resolution of an AE or finding may be appended to the CSR.

The overall study design is shown in the figure below.

Figure 1 ARCT 165-01 Study Schema

3.2 Schedule of Assessments

For the complete schedule of assessments, refer to Appendix 1 (for Cohort A) and Appendix 2 (Cohort B) of the clinical study protocol.

3.3 Study Vaccines

3.3.1 Study Vaccines Administered

The following three study vaccines will be administered:

- ARCT-021: A self-amplifying RNA vaccine coding for wild-type ancestral strain spike antigen;
- ARCT-154: A self-amplifying RNA vaccine coding for the D614G variant of ancestral strain spike antigen; and
- ARCT-165: A self-amplifying RNA vaccine coding for the B.1.351 variant of SARS-CoV-2 and also containing the D614G variant mutation.

Study vaccines are LNP-formulated, RNA replicon vaccines. The study vaccines are provided as lyophilized formulations in multi-dose glass vial presentations. Study vaccines will be matched for volume (0.5 mL) and presentation (1-mL syringe) prior to administration, and will be administered by intramuscular injection to the deltoid muscle by a health care provider who will not be involved in assessments of any study endpoints.

Participants in Sub-cohort A1 (vaccine-naïve, seronegative) will receive two 5-µg doses of ARCT-165, ARCT-154, or ARCT-021. Participants in Sub-cohort A2 (vaccine-naïve, seropositive) will receive two 5-µg doses of ARCT-154 or ARCT-021. Participants in Sub-cohorts A1 and A2 will receive the first dose on Day 1 and the second dose on Day 29. Participants in Cohort B (previously vaccinated) will receive a single dose of ARCT-165, ARCT-154, or ARCT-021 on Day 1.

3.3.2 Method of Assigning Participants to Study Vaccine Groups

Participants will be enrolled in two distinct cohorts based on previous vaccination status Cohort A (vaccine-naïve) and Cohort B (previously vaccinated). Cohort A will be further subdivided into two sub-cohorts (Sub-cohort A1 – seronegative, Sub-cohort A2 – seropositive).

All participants will be randomized after all screening assessments have been completed, and after the Investigator has verified that they are eligible per criteria in Sections 4.1.1 and 4.1.2 of the clinical study protocol. Sub-cohort A1 and Cohort B participants will be randomized in a 1:1:1 ratio to one of three study vaccines (ARCT-165, ARCT-154, or ARCT-021). Sub-cohort A2 participants will be randomized in a 3:1 ratio to one of two study vaccines (ARCT-154 or ARCT-021).

Arcturus Therapeutics or designee will prepare the randomization list, which will be provided to the study site unblinded pharmacist.

3.3.3 Blinding Procedures

The study vaccines will be administered in an observer-blind fashion.

Each of the study vaccines will be prepared by an unblinded trained team member and in accordance with the Pharmacy Manual.

Unblinded personnel (of limited number) will be assigned to study vaccine accountability procedures and will prepare study vaccine for all participants. These personnel will have no study functions other than study vaccine management, documentation, accountability, preparation, and administration. They will not be

involved in participant evaluations and will not reveal the identity of study vaccine to either the participant or the blinded study site personnel involved in the conduct of the study unless this information is necessary in the case of an emergency.

- The health care provider who administers the study vaccine will not be involved in assessments of any study endpoints.
- Unblinded site monitors not involved in other aspects of monitoring will be assigned as the study vaccine accountability monitors. They will have responsibilities to ensure that sites are following all proper study vaccine accountability, preparation, and administration procedures.

In order to maintain an observer-blind design, Investigators, site staff, participants, and contract research organization staff with oversight of study conduct will remain blinded to study vaccine assignments for the study duration. The Arcturus Therapeutics team with direct oversight of the study will remain blinded to individual participant study vaccine assignments until the time of study unblinding at the final analysis. All study participants will be followed for efficacy and safety endpoints through the planned study period, and results will be summarized in an end of study report.

Arcturus Therapeutics staff who are not involved in direct oversight of the study may receive unblinded study data but will not share any unblinded information with the Arcturus Therapeutics team members overseeing the study.

3.4 Immunogenicity, Safety, and Other Variables

3.4.1 Immunogenicity Variables

3.4.1.1 Primary Immunogenicity Variables

The primary immunogenicity endpoints include:

- SARS-CoV-2 neutralizing antibody titer by pseudoviral microneutralization assay (ancestral strain, D614G variant, and B.1.351 [Beta] variant [as available]) from the PPD Laboratory. Assay results will be evaluated as follows:
 - Geometric mean concentrations (GMCs) at each time point designated in the schedule of assessments;
 - Geometric mean fold rise (GMFR) from baseline (pre-vaccination blood samples drawn Day 1) to each subsequent time point evaluated after vaccination;
 - Proportion of participants achieving ≥ 4 -fold rise in titer from baseline (pre-vaccination blood samples drawn Day 1) to each subsequent time point evaluated after vaccination; and
 - GMC ratio (ARCT-021/ARCT-165, ARCT-165/ARCT-154, and ARCT-021/ARCT-154 where applicable) measured at all time points evaluated.

- Binding antibody titer: Immunoglobulin G (IgG) to variant-specific SARS-CoV-2 full-length spike, receptor-binding domain (RBD), and N antigens measured by Meso Scale Discovery (MSD) multiplex assay from the PPD Laboratory (ancestral strain, D614G variant, and B.1.351 [Beta] variant, as available):
 - Geometric mean concentrations (GMCs) at each time point designated in the schedule of assessments;
 - GMFR from baseline (pre-vaccination blood samples drawn Day 1) to each subsequent time point evaluated after vaccination; and
 - Proportion of participants achieving ≥ 4 -fold rise in GMC from baseline (pre-vaccination blood samples drawn Day 1) to each subsequent time point evaluated after vaccination.

3.4.1.2 *Exploratory Immunogenicity Variables*

The cell-mediated immune responses to different variants of SARS-CoV-2 following vaccination is an exploratory immunogenicity endpoint. It will be measured at designated time points using one or more of the following assays:

- ELISpot (Oxford Immunotec T-spot) assay assessing IFN- γ secreting T cells (spots/ 10^6 PBMCs);
- Intracellular Cytokine Staining (ICS) assay assessing IFN- γ , TNF- α , IL-2, IL-4, IL-5, and IL-13 expressing CD4+ and CD8+ T cells; or
- Fc effector function: Antibody-mediated cytotoxicity will be measured using surrogate assays measuring CD16 signaling at some or all time points designated in the schedule of assessments.

The SARS-CoV-2 neutralizing antibody titer by pseudoviral microneutralization assay (B.1.617.2 [Delta], and BA.1 [Omicron]) from the PPD Laboratory, as well as the neutralizing antibody titer by pseudoviral microneutralization assay (D614G, B.1.617.2 [Delta], B.1.351 [Beta], and BA.1, BA.2, and BA.4/5 [Omicron]) from the [name] Laboratory (as available) will also be evaluated using similar methods as described for other variants in [Section 3.4.1.1](#). For the [name] Laboratory assays, data will be evaluated using geometric mean titers (GMTs).

The binding antibody titers measured by MSD multiplex assay (Spike [P.1], Spike [B.1.1.7]) and the ACE2 Panel 13 (SARS-CoV-2 Spike, SARS-CoV-2 Spike [B.1.1.7], SARS-CoV-2 Spike [B.1.351], SARS-CoV-2 Spike [B.1.526.1], SARS-CoV-2 Spike [B.1.617], SARS-CoV-2 Spike [B.1.617.1], SARS-CoV-2 Spike [B.1.617.2], SARS-CoV-2 Spike [B.1.617.3], SARS-CoV-2 Spike [P.1], SARS-CoV-2 Spike [P.2]) from the PPD Laboratory, will also be evaluated using similar methods as described for other variants in [Section 3.4.1.1](#).

Additional exploratory immunogenicity analyses may be performed for other emerging COVID-19 variants.

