	
adverse events (SAEs) through Final Visit/Early Termination (ET) Visit (Final Visit is defined as 365 days after the last study vaccine dose)
 
Objective 2: To describe the immunogenicity (antibody responses) of 3 investigational SARS-CoV-2 self-amplifying RNA vaccines
 
Immunogenicity (antibody responses) will be evaluated after vaccination using the following assays and approaches:
 
Endpoint 2: SARS-CoV-2 neutralizing antibody titer by pseudoviral microneutralization assay (ancestral strain, D614G variant, and SARS-CoV-2 Betavariant [as available]). Assay results will be evaluated as follows:
 
 Geometric mean concentrations (GMCs) at each time point designated in the Schedule of Assessments. Geometric mean fold rise (GMFR) from before vaccination to each subsequent time point evaluated after vaccination. Proportion of participants achieving ≥ 4-fold rise from before vaccination to each subsequent time point evaluated after vaccination. GMC ratio (ARCT-021/ARCT-165, ARCT-165/ARCT-154, and ARCT-021/ARCT-154) measured at all time points evaluated. Exploratory: Neutralizing antibody responses to other SARS-CoV-2 variant strains may also be performed and will be described in the statistical analysis plan (SAP). 
Endpoint 3: Binding antibody concentration: Immunoglobulin G (IgG) to variant-specific SARS-CoV-2 full-length spike, receptor-binding domain (RBD), and nucleocapsid (N) antigens measured by Meso Scale Discovery (MSD) multiplex assay (ancestral strain, D614G variant, SARS-CoV-2 Beta variant, as available) will be evaluated as follows:
 
 Geometric mean concentrations (GMCs) at each time point designated in the Schedule of Assessments. GMFR from before vaccination to each subsequent time point after vaccination. Proportion of participants achieving ≥ 4-fold rise from before vaccination to each subsequent time point after vaccination. Exploratory: Binding antibody responses to other SARS-CoV-2 variant strains may also be performed and will be described in the SAP.

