1.4 Mechanism of Action

ARCT-021, ARCT-154, and ARCT-165, each contain Arcturus' proprietary self-transcribing and -replicating RNA (STARRTM) technology, an RNA replicon construct based on the alphavirus, Venezuelan equine encephalitis virus (VEEV). The replicon for ARCT-021 (mRNA-2002) consists of a replicase gene and an RNA sequence encoding the ancestral strain SARS-CoV-2 S glycoprotein. The replicon for ARCT-165 (mRNA-2106) consists of a replicase gene and an RNA sequence encoding the SARS-CoV-2 S glycoprotein containing the SARS-CoV-2 Beta variant mutations (D80A, D215G, E484K, K417N, N501Y, and A701V) and, additionally, the D614G variant mutation. The replicon for ARCT-154 (mRNA-2105) consists of a replicase gene and an RNA sequence encoding the SARS-CoV-2 S glycoprotein containing the D614G variant mutation. The final drug product for all 3 vaccines includes an RNA replicon formulated with Arcturus' proprietary lipid nanoparticle (LNP) technology (LUNAR[®]), including 4 lipid excipients. More detail relating to these vaccines is included in the Investigator's Brochure (IB) (Arcturus 2022a).

Alphaviruses are enveloped viruses with a positive strand RNA genome. Upon infection, the genomic RNA serves as a template for translation of 4 viral nonstructural proteins that form replicase complexes. These complexes synthesize viral genomic and subgenomic RNA, the latter of which serves as a template for translation of viral structural proteins, which then assembles with genomic RNA into new infectious viral particles. By replacing the RNA coding for structural proteins with RNA coding for a protein antigen of interest (in this case, the SARS-CoV-2 full-length S glycoprotein), the self-replicating machinery of the alphavirus can be used to generate sustained expression of the antigen, making such alphavirus replicon constructs an attractive tool for vaccines. These replicon RNAs, which do not encode the complement of structural genes necessary for assembly of virus particles and do not contain reverse transcriptase that converts the RNA genome into complementary deoxyribonucleic acid (DNA), replicate exclusively in the cytoplasm and cannot introduce their genetic material into the cellular genome. A more detailed description of the mechanism of mRNA amplification and the biochemical functions for each of the nonstructural proteins is described in Rupp 2015.

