2 STUDY OBJECTIVES AND ENDPOINTS

2.1 Primary Objectives and Endpoints

The primary objective(s) and endpoints are presented in [Table 2](#).

Table 2 Primary Objectives and Endpoints

Primary Objectives	Endpoint Description
1. To describe the safety and reactogenicity of 3 investigational SARS-CoV-2 self-amplifying RNA vaccines	
Endpoint 1: Safety will be summarized for each vaccination as the number and percentage of participants with the following:
 
d. Any solicited local or systemic AE collected for 7 days after each study vaccination, which will be assessed by toxicity gradee. Any unsolicited AE collected for 28 days after each study vaccination, which will be assessed by severity and relationship to study vaccinef. Any MAAEs, AEs leading to discontinuation from study vaccine/study withdrawal, or SAEs through Final Visit/ET Visit (Final Visit is defined as 365 days after the last study vaccine dose)
2. To describe the immunogenicity (antibody responses) of 3 investigational SARS-CoV-2 self-amplifying RNA vaccines	
Immunogenicity (antibody responses) will be evaluated after vaccination using the following assays and approaches:
 
Endpoint 2: SARS-CoV-2 neutralizing antibody concentrations by pseudoviral microneutralization assay (ancestral strain, D614G variant, and SARS-CoV-2 Beta variant [as available]). Assay results will be evaluated as follows:
 
a. GMCs at each time point designated in the Schedule of Assessments (Appendix 1 and Appendix 2).b. GMFR from before vaccination to each subsequent time point evaluated after vaccination.c. Proportion of participants achieving ≥ 4-fold rise from before vaccination to each subsequent time point evaluated after vaccination.d. GMC ratio (ARCT-021/ARCT-165, ARCT-165/ARCT-154, and ARCT-021/ARCT-154) measured at all time points evaluated.e. Exploratory: Neutralizing antibody responses to other SARS-CoV-2 variant strains may also be performed and will be described in the SAP. 
Endpoint 3: Binding antibody concentration: IgG to variant-specific SARS-CoV-2 full-length spike, RBD, and N antigens measured by MSD multiplex assay

Table 2 Primary Objectives and Endpoints

Primary Objectives	Endpoint Description

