Unless otherwise noted (e.g. immunogenicity data handling rules), values reported as greater than or less than some quantifiable limit (e.g., “< 1.0”) will be summarized with the sign suppressed in summary tables and figures, using the numeric value reported. Data will display on participant listings to include the sign.

4.1.4 *Standard Calculations*

Where appropriate, the calculated study day of each assessment or event will be presented with the assessment or event date on participant data listings, where study day will be determined as:

- The assessment/event date minus the date of first dose of study vaccine, if the assessment/event date is prior to the date of first dose of study vaccine; and
- The assessment/event date minus the date of first dose of study vaccine, plus one, if the assessment/event date is on or after the date of first dose of study vaccine.

Other variables requiring calculations will be derived using the following formulas:

- **Days:** A duration between two dates expressed in days will be calculated using the following conventions:
 - Later date – earlier date + 1, if the earlier date is on or after the date of first dose of study vaccine; or

- Later date – earlier date, if the earlier date is prior to the date of first dose of study vaccine.
- **Months:** A duration expressed in months will be calculated by dividing the duration in days by (365.25 / 12).
- **Years:** A duration expressed in years will be calculated by dividing the duration in days by 365.25.
- **Change from Baseline:** Change from baseline will be calculated as the post baseline value minus the baseline value.
- **Percentage Change from Baseline:** Percentage change from baseline will be calculated as the change from baseline divided by the baseline value, multiplied by 100.
- **GMC/GMT:** Calculated as the anti- $\log_{10}(\text{mean}[\log_{10}X_i])$, where X_i is the assay concentration/titer result for participant i .
- **GMFR:** Calculated as the anti- $\log_{10}(\text{mean}[\log_{10}Y_i/B_i])$, where Y_i is the post dose assay result for participant i ; and B_i is the baseline assay result for participant i .
- **Seroconversion (Cohort A):** Proportion of participants achieving ≥ 4 -fold rise from before vaccination to each subsequent time point evaluated after vaccination.
- **Seroresponse (Cohort B):** Proportion of participants achieving ≥ 4 -fold rise from before vaccination to each subsequent time point evaluated after vaccination.

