4.5.2 Primary Immunogenicity Endpoint Analysis Methods

Immunogenicity endpoints as described in [Section 3.4.1.1](#) will be summarized by study vaccine group and visit using descriptive statistics for each cohort.

The number and percentage of participants with non-missing titers will be presented for each visit. Geometric mean concentrations and GMFRs will be summarized and presented, along with corresponding 95% student t CIs. The proportion of participants achieving a ≥ 4 -fold rise (seroconversion for Cohort A or seroresponse for Cohort B) from before vaccination to each subsequent time point evaluated after vaccination will also be presented, along with corresponding 95% Clopper-Pearson exact CIs.

For the D614G MNT assay, results may be presented in IU/mL in addition to AU/mL with a conversion of 1 IU/mL = 1.275 AU/mL. For GMC calculations, antibody titers below the lower limit of quantification (LLOQ) will be set to half that LLOQ value for the purposes of analysis. For seroconversion (Cohort A) and seroresponse (Cohort B), LLOQ values will be set to the LLOQ value. Missing values will be excluded from analysis.

Box and whisker plots will be generated to display the distribution of titers separately for each study vaccine group and antigen, for both baseline and post-baseline time points. Additional graphical representations of immunogenicity data, including (but not limited to) reverse cumulative frequency plots, may also be provided.

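### Nucleocapsid IgG sits in the primary vaccine-response endpoint of spike-only vaccines, so a ≥4-fold N rise from an unconfirmed infection is labelled seroconversion or seroresponse

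*SAP*

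**What the plan says.** Primary objective 2 is to describe the antibody response to the three vaccines. Under it, protocol Table 2 (Endpoint 3) lists "IgG to variant-specific SARS-CoV-2 full-length spike, RBD, and N antigens measured by MSD multiplex assay", and SAP 3.4.1.1 repeats the three antigens in one primary bullet: "full-length spike, receptor-binding domain (RBD), and N antigens measured by Meso Scale Discovery (MSD) multiplex assay". All three get a GMC, a GMFR and a ≥4-fold-rise proportion.

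SAP 4.1.4 defines seroconversion and seroresponse identically, as the proportion with the required "fold rise from before vaccination to each subsequent time point evaluated after vaccination". SAP 4.5.2 carries the labels into the primary analysis: "The proportion of participants achieving a ≥ 4 -fold rise (seroconversion for Cohort A or seroresponse for Cohort B) from before vaccination". Neither section limits the label by antigen.

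Protocol 1.4 describes the constructs. ARCT-021 "consists of a replicase gene and an RNA sequence encoding the ancestral strain SARS-CoV-2 S glycoprotein"; ARCT-165 carries "an RNA sequence encoding the SARS-CoV-2 S glycoprotein containing the SARS-CoV-2 Beta variant mutations" and also D614G; ARCT-154 carries "an RNA sequence encoding the SARS-CoV-2 S glycoprotein containing the D614G variant mutation".

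Three other provisions bear on the point:
- SAP 4.5.1 cuts a participant's immunogenicity data at the last visit before a confirmed COVID infection.
- Protocol 7.5.4 commits to immunogenicity sensitivity analyses that include and exclude participants who test N-positive on study.
- SAP 4.8.1.7 makes that analysis optional and ties it to participants seronegative at baseline, while SAP 4.10 reports no change from the protocol's planned analyses.

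**The concern.** The plan gives one measurement two incompatible meanings. For eligibility and sensitivity analysis, N antibody shows past or new infection. In the primary binding-antibody tables, a ≥4-fold rise in the same antibody carries a vaccine-response label, by vaccine group, beside spike and RBD. Since no vaccine encodes N, such a rise is not a response to the vaccine antigen.

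At stake are the reading of a primary table in very small arms and the use made of the N data. SAP 4.7 counts confirmed COVID-19 cases, and adds suspected ones in a sensitivity analysis. It makes no use of N rises, which could show infections that nobody suspected or tested for.

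**Working it through.** **1. Can an N rise be a vaccine response?** Protocol 1.4 gives each replicon a replicase gene (from an alphavirus) and a spike sequence, and names full-length spike as the vaccine antigen. Nucleocapsid appears in none of them.

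**2. How does the protocol use N elsewhere?** A positive N test is required for Sub-cohort A2 (inclusion 7), excludes from A1 in South Africa and the US (exclusion 19), and defines the sensitivity groups in 7.5.4. Each use treats N as evidence of infection.

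**3. Which infections reach the N responder table?**
- Confirmed: data after the last pre-infection visit are removed (SAP 4.5.1).
- Unconfirmed: data stay. Testing follows symptoms or known exposure (protocol 6.7), and Appendices 1 and 2 schedule a SARS-CoV-2 sample only at unscheduled visits. SAP 3.4.3 ties virological confirmation to a positive laboratory test, and protocol Appendix 7 describes RT-PCR or another nucleic acid test. N serology is not listed, so I read an N rise alone as not triggering the censoring.
- A2: everyone is N-positive at screening, so a ≥4-fold rise mainly suggests reinfection.

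**4. Does the N-positive sensitivity analysis repair this?** It can protect the spike, RBD and neutralization results. For N itself it is close to circular, because dropping those who become N-positive largely drops the N responders. It cannot separate participants in A2, where all start positive, and the SAP version leaves A2 out.

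**5. Size of one event.** The plan states no N responder rate and no sample size calculation. The only figure to reproduce is enrolment: A1 12/3 = 4 per arm; A2 24 × 3/4 = 18 and 24 × 1/4 = 6; Cohort B 36/3 = 12 per arm. Total 12 + 24 + 36 = 72, as stated.

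One infection-driven rise present at a visit adds 100 × 1/n percentage points. The intervals are the Clopper-Pearson 95% CIs named in SAP 4.5.2, for one responder.

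| Arm | n | 100/n | 95% CI for 1/n |
|---|---|---|---|
| A1, each vaccine | 4 | 25.0 | 0.6 to 80.6 |
| A2, ARCT-021 | 6 | 16.7 | 0.4 to 64.1 |
| Cohort B, each vaccine | 12 | 8.3 | 0.2 to 38.5 |
| A2, ARCT-154 | 18 | 5.6 | 0.1 to 27.3 |

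These use full planned arms. SAP 4.1.1 takes percentages over participants with available data, so missing or censored results make n smaller and the step larger.

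**6. Why no expected number is given.** Purely as an assumption, let 5% to 30% be infected during follow-up, with 25% to 50% of those infections unconfirmed and each giving a ≥4-fold rise. The per-person probability q is then 0.05 × 0.25 = 0.0125 to 0.30 × 0.50 = 0.15. The chance of at least one in a 12-person arm, 1 − (1 − q)^12, runs from 14.0% to 85.8%. That is cumulative over follow-up, whereas the plan's proportions are per visit. The range is too wide to support a forecast.

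**The case against.** The strongest reply is that this is labelling in a descriptive study. No formal hypothesis test or formal group comparison is planned, so no error rate is affected. The GMC ratio is specified for neutralizing antibody only, N is not combined with spike or RBD, and the listings generally show all collected data. SAP 4.1.4 defines both labels operationally, and no passage says the vaccines induce N antibody. An expert reader would probably recognise N as an infection marker. All of that stands and limits the weight of the point. It does not explain why an infection marker belongs in a primary vaccine-response endpoint.

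Three stronger readings are tempting, and the documents do not support them:
- *Every infection during the study would appear as an N responder.* SAP 4.5.1 removes post-infection data for confirmed cases.
- *The censoring hides the undetected infections.* It removes only confirmed ones. Undetected infections remain in the table, and the problem is the heading under which they appear.
- *A material share of each arm will be misclassified.* Neither document gives an infection rate or an unconfirmed share, and a cumulative 12-month figure would overstate a single visit unless every rise persisted. In A2 the rise must also build on an existing titre.

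It is also fair that protocol 7.5.4 already plans an N-based sensitivity analysis. As shown above, it serves the other antibody endpoints and not the N table, and the SAP has weakened it.

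**Conclusion.** The point holds in this form. N IgG is in the primary vaccine-response endpoint of both documents, and a ≥4-fold N rise takes the seroconversion or seroresponse label although spike is the only SARS-CoV-2 antigen encoded. With confirmed infections censored, that rate would capture mainly unconfirmed infections, and reinfections in A2. Each one moves an arm's rate at that visit by 5.6 to 25.0 points, depending on the arm.

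This assumes that a ≥4-fold N rise after dosing comes from infection, and that N serology alone does not count as confirmation under SAP 4.5.1. How many such rises will occur cannot be derived from the documents. The consequence is one of interpretation and of under-used infection data. The spike, RBD and neutralization summaries are not altered by the N table, and no power or alpha is involved. It is worth correcting because the data already exist and the change is small.

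**What to change.** 1. Remove N from the vaccine-response analyses in SAP 3.4.1.1 and 4.5.2, stop applying seroconversion or seroresponse to it, and edit protocol Endpoint 3 to match.
2. Report N IgG as an infection marker under exploratory objective 2: the number with a ≥4-fold N rise, by vaccine group, in all dosed participants (the Safety Set), without the SAP 4.5.1 censoring, split by whether a case was confirmed.
3. In SAP 4.8.1.7, make the N-based sensitivity analysis of the spike, RBD and neutralization results mandatory, as in protocol 7.5.4. In Sub-cohort A2, identify infections by a ≥4-fold N rise, since N positivity does not distinguish participants there.

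The cost is one fewer antigen in the primary endpoint list, one relocated table, SAP wording and a small protocol amendment. Protocol section 7 provides for an amendment when primary objectives or their methods change before unblinding. No new samples or assays are needed, because the multiplex assay already measures N at the scheduled immunogenicity visits.
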